6.2.2 Nutritional intervention

The aim of the nutritional part of the intervention is avoidance of sub-optimal pre-operative nutritional intake. All participants will receive the pre-operative nutritional advice as part of usual standard of care. In addition, all participants in the intervention arm will be encouraged to follow these guidelines as part of the adherence support. The usual care regarding nutritional advice in the period before CABG surgery include weight maintenance, intake of energy and protein rich food items as well as micronutrients with focus on a daily intake of B and C vitamins. The patients are advised to plan their meals if the appetite is low to ensure a sufficient intake of protein and energy before the surgery which is considered more important in the pre-operative period than following the general advice regarding consumption of vegetables etc. Energy and protein rich supplements are also suggested for patients with low appetite to promote an energy and protein rich diet in the pre-operative period. Nutritional risk will be assessed at baseline and preoperatively using the NRS-2002 total score which is already part of usual care.⁷⁸ After screening with NRS-2002 patients are categorized as being nutritionally at-risk patients (score>3) or nutritionally not at risk (score<3) according to the total score obtained. Patients not at risk for malnutrition will be provided with nutritional advice according to usual care. In addition to usual care regarding nutrition, not at-risk patients will receive encouragement to follow the nutritional advice as part of adherence support throughout the intervention period. In addition to usual care at-risk patients will be offered protein and energy rich supplements free of charge as well as individualized advice and encouragement as part of adherence support throughout the intervention period.

6.2.3 Psycho-educative intervention

The intervention seeks to enhance preparedness for CABG surgery through individualized assessment and review of psychosocial factors that may influence treatment outcomes and quality of life. Mental health such as emotional well-being and stress reduction will serve as primary foci of this psycho-educative intervention inspired by Antonovsky' s salutogenetic theory known as Sense of Coherence (SOC).⁷⁹ The SOC is composed of three key components: comprehensibility, manageability, and meaningfulness. According to Antonovsky, a strong SOC enables individuals to view stressors as less threatening and more manageable, thereby promoting resilience and health. Depending on the patients' SOC, when going through a negative life event as living with IHD awaiting CABG surgery, the intervention aims to support in terms of understanding and involve the availability of the patients' resources to deal with these events. By identifying appropriate resources to cope with stress and encourage the patient to use these resources, making the waiting period before heart surgery more understandable, manageable, and meaningful. Involving SOC-enhancing content

in this intervention we are inspired by theory of psycho-educative programs.^{80, 81} Nurses play a pivotal role in delivering psychosocial support to patients undergoing cardiac surgery⁸² and in this intervention it will be provided by trained nurses, who will engage in counselling sessions aimed at equipping patients with coping strategies to mitigate stress, anxiety, and depression.⁸³ The preoperative baseline consultation will take place in a quiet room in the ward and last for about 30-45 minutes. An inspirational guide will form the basis for the consultations. There will be consultation: at study inclusion, and once a week (by phone) in the waiting period until the day before surgery. The participants will be given a phone number to the responsible project nurse, who can be contacted in a certain period on working days.

6.2.4 Smoking cessation intervention

In this intervention, patients will receive guidance on smoking cessation. During these sessions, a nurse will educate the patient about the detrimental effects of smoking on the development and progression of ischemic heart disease, emphasizing the negative impact of smoking on their health, particularly before surgery, where smoking cessation is strongly recommended.⁸⁴ As part of the intervention, patients will be encouraged to contact the municipal smoking cessation coordinators to arrange a meeting and receive further support. The smoking cessation program will include counselling sessions at baseline and weekly phone call sessions, along with the provision of nicotine replacement therapy (NRT). NRT will be provided in the form of transdermal patches for moderate to heavy smokers, supplemented with individualized doses of chewing gum or lozenges, following current guidelines.⁸⁵ NRT will be distributed during the baseline counselling session. The objective of the program is to achieve an 80% reduction in smoking quantity (cigarettes per day) before surgery or complete cessation.

6.2.5 Alcohol cessation intervention

The approach to support patients in zero alcohol intake before surgery is rooted in the recommendations from the Danish Health Authority and the patients are encouraged to completely avoid alcohol intake if the patient is assessed a risky drinker (drinking more than 4 alcohol items per day).⁸⁶ A simple guide of questions and advice will be developed for the adherence support to register challenges and encourage adherence to support minimizing/avoiding alcohol intake. Assessment, counseling, and support sessions will be organized with the social nurse at Rigshospitalet for patients exhibiting hazardous drinking behaviors.

After the initial face-to-face meeting in the pre-clinic participants will receive three web-based sessions with a physiotherapist and one telephone counselling with a nurse per week during the intervention period. Detailed protocols for the face-to face counselling and web-based and telephone calls will be developed before the outset of the study.

7. Study outcome measures

In this CABGpreHAB feasibility study we will explore two types of outcomes: feasibility outcomes and explorative clinical outcomes.

7.1 Primary outcome

Feasibility outcomes include:

Recruitment and retention rates. The recruitment rate will be determined by the number of individuals who participate in the study out of those who are eligible/admissible but refused to participate. First, we will evaluate the number of patients we are able to include in the study during the inclusion period. A proportion of 60% or more of patients awaiting elective CABG surgery who are eligible for the study is acceptable. Retention will be assessed by the percentage of participants who remain in the study from beginning to end of study (30 days post-surgery).

Attrition rates. Attrition is defined by the number of individuals who give consent to participate in the study but drop out before the end of the intervention period, regardless of group allocation.

Fidelity. Fidelity of delivery of the webcam-based exercise training intervention will be assessed qualitatively by 8-10 semi-structured interviews the day before surgery by a research nurse.

Adherence rates. Adherence to the interventions will be measured by using the number of telephone counselling and tele-exercise sessions delivered out of the theoretical number that could have been delivered based on the surgical wait time of each participant. Adherence to the homebased tele-exercise training sessions and telephone counselling by evaluating the number of sessions applied in the intervention group. This will be collected by patient recorded physical activity logbook, by weekly phone calls and completed by accelerometer data. Adherence with the prehabilitation program will be assessed against the target of individuals achieving > 70% of the prescribed exercise program (self-reported) + during the study follow-up with phone calls. Inclusion in the CABGpreHAB study must be attractive to at least 30% of eligible patients who meets the inclusion criteria. The interventions must be widely accepted, with at least 70% of included participants completing 70% or more of the planned sessions in the intervention group. This will be assessed by interviews addressing reasons for withdrawals from the study and at which stage of the study these occur.

Safety: Safety of the intervention will be determined based on the number and nature of adverse events (AE), which is defined as any discomfort or symptoms of angina pectoris that will prevent a patient to take part in the physical tele exercise sessions or symptoms that require medical attention. Adverse event (AE), serious AE (SAE), serious adverse reaction (SAR), and suspected unexpected serious adverse reaction (SUSAR) will be monitored during the trial counting the number of occurrences. In addition to the physiotherapist

taking note of any undesirable effect during and after the tele session or phone counselling with the project nurse, all participants are asked to report any symptoms that was not consistent with their usual physical condition presentation as a result of exercise sessions.

For a lager RCT trial to be deemed feasible, feasibility outcomes need to be attained, meaning that more than 60% of eligible patients will participate and at least 52% of the intervention group will receive more than 60% of the intended interventions.⁸⁷

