2.1 Primary objective

The primary objective of this feasibility study is to determine if it is feasible for patients awaiting elective CABG surgery to participate in a preoperative homebased multimodal prehabilitation intervention. We will evaluate this through completion of the following objectives:

- Assess the proportion of eligible patients that are recruited into the study.
- Assess the suitability of inclusion and exclusion criteria by examining recruitment data.
- Explore reasons for non-consent to study participation.
- Assess the acceptability of the study to patients by measuring recruitment and retention to the study and thorough qualitative interview responses.
- Assess the acceptability of the intervention through qualitative interviews and retention rates during the study.
- Assess adherence to and completion of the intervention (i.e. do participants adhere and work through all components of the intervention) and explore engagement and satisfaction with the interventions by qualitative interviews.
- Assess the proportion of patients lost to follow-up after study entry.
- Assess safety of the interventions.
- Explore the appropriateness of outcome measures, completion rates and assess response to questionnaires through qualitative interviews.
- Evaluate the logistics of delivering a home-based tele-exercise training intervention through qualitative interview responses from both health care professionals and patients.
- Determine the “prehabilitation window” (length of time between MDT-conference and CABG surgery)

2.2 Secondary objective:

The secondary objectives will evaluate if the multimodal prehabilitation intervention has an impact on preoperative and postoperative outcomes. For this we will collect data on study outcomes to assess levels, variation, and changes over time, which can inform sample size for the future RCT, as shown in **Table 1**, section 7.2.

3. Method

[figure not shown]

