3.6 Sample size and power

As the primary aim of this study is to evaluate feasibility, there is no formal requirement for a formal power calculation.⁶² Sample sizes between 24 and 50 have been recommended.^{63,64} A sample size of 25 patients in each group was chosen as it seems reasonable to provide outcome data in a small sample, and at the same time a sample size large enough to investigate the additional aspects that are being assessed for feasibility⁶⁵ informing a future power calculation for a full-scale RCT.

4. Selection and allocation of participants

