Following the MDT conference in the department of Heart and Lung Surgery, Rigshospitalet the responsible surgeon screen for eligibility by comparing patients' referral against the inclusion and exclusion criteria as described in this protocol section 4.1. If the patient is deemed eligible after screening, they will receive an invitation in e-Boks to be contacted for a brief information about the study. If they accept this invitation, the patient will be contacted by telephone by a responsible clinician in the project, and if the patient is interested to hear more, written information material about the study will be send by e-Boks or regular post. The patient will be informed that participating is voluntary, that they have the right to bring a bystander for the oral information, which will take place when they meet for the planned visit in the pre-clinic some days later. If patients haven't got the invitation about information in E-boks the responsible surgeon will introduce the study for eligible patients and present patients with the written information at the meeting in the pre-clinic. The oral information will be given with no external interruptions and will be given in a language easily understood without technical or value laden terms. The patient will receive a full explanation of the study design and study procedures, and information about usual care. This information interview is performed by the principal investigator or in her absence by a designated delegate. Consent to participation is given on the basis of written and oral information. Prior to consent, it must be ensured that a potential participant has been given sufficient time to consider his or her participation and minimum 24 hours. However, potential participants can sign earlier if they wish. An informed consent form must be signed and dated by the participant prior to participation in the trial. A copy of the form is provided to the participant. The principal investigator and her designated delegates can receive the signed consent form. When the written informed consent is received, the study specific procedures such as test, randomization and other study related procedures will take place.

Patients will be eligible if they comply with the inclusion criteria in line with previously used criteria.^{66,67} Exclusion criteria are listed below.

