4.2 Exclusion criteria

- Patient with unstable angina pectoris and/ or MI during the last two weeks.
- Left main stem stenosis >50%
- Left ventricular ejection fraction < 35%
- Significant ventricular arrhythmia
- Orthopedic or neurologic preconditions precluding exercise training.
- Inability to attend the prehabilitation program due to physical limitations.
- Patients who have cognitive deficits that would disqualify prehabilitation.
- Severe heart failure, NYHA Class IV
- Lack of capacity to consent

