9.1 Statistical methods

Data analysis will be limited to descriptive summary statistics of the proposed endpoints, and calculation of feasibility measures, enrollment rates and dropout rates within a period. The feasibility analysis will be based on the components of process, resources, management, and scientific approach.⁵⁸ Process: number of eligible patients for enrollment; Successful recruitment rate, rate of adherence to the interventions at each time point; Rate of loss to follow up; Rates of completed questionnaires; Understanding of the questionnaires. Resources: Time to screen and consent patients, Time to conduct baseline and follow-ups; Identification of any challenges related to randomization or data collection; Identification of potential barriers of the preoperative programme. Management: Identification of any challenges related to randomization or data collection; Identification of potential barriers for the intervention. Scientific approach: Estimates of improvement in patient-reported outcomes compared to usual care, patients' response to topics and content in the programme and identification of potentially patient safety issues. As recommended for the analysis of pilot studies⁵⁸ descriptive statistics will be presented as mean and standard deviations (SD) for continuous variables and frequencies and percentages for categorial variables at baseline and follow-ups. Collected data on patient characteristics will be presented in tables. Continuous variables will be displayed as mean (SD), while categorical variables will be presented as number (n) and percentage (%). Descriptive statistics will be used to answer the primary study parameter of feasibility. Feasibility will be presented in tables and based on participation rate (n, %), reasons for nonparticipation (n, %, text), adherence to the prehabilitation program (%), dropout rates (%), reasons for dropout (n, %, text), adverse events (n, %, text). The secondary aim is to evaluate the patients' responses over time in terms of physical activity, muscle strength, functional capacity, body composition, quality of life and symptoms of depression, and anxiety. A repeated measurements analysis will be used to analyze changes over time in continuous variables. *P*- values <0.05 will be considered statistically significant.

10. Ethics

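### Section 7.1 defines the recruitment rate over eligible patients who refused, which is an odds if read literally and conflicts with Section 2.1 and the progression rule

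*Protocol*

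**What the plan says.** Section 7.1 lists recruitment first among the feasibility outcomes and defines the rate as the "number of individuals who participate in the study out of those who are eligible/admissible but refused to participate".

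Two other places describe the same quantity with a different denominator:

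- Section 2.1, first item under the primary objective: "Assess the proportion of eligible patients that are recruited into the study".
- Section 7.1, closing paragraph, which states when a larger RCT is deemed feasible: "feasibility outcomes need to be attained, meaning that more than 60% of eligible patients will participate".

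Section 9.1 plans the reporting: "Feasibility will be presented in tables and based on participation rate (n, %), reasons for nonparticipation (n, %, text"). It gives no denominator for the participation rate, although it also lists the number of eligible patients among the process measures.

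**The concern.** Nobody both takes part and refuses, so the denominator written in 7.1 contains none of the people in the numerator. The result is participants relative to refusers, not a share of eligible patients. It does not match the objective it is meant to answer or the rule it is meant to inform, and no other section corrects it.

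Recruitment is a primary outcome and one of the two quantitative criteria in the progression rule. Anyone programming or reporting the rate from its definition would publish a figure that is too high. If that figure were also the one held against 60%, recruitment could pass at an uptake well below what the rule asks for.

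**Working it through.** The protocol calculates nothing from this definition and gives no expected number of eligible or refusing patients, so there is no figure to reproduce. The check compares the two definitions algebraically.

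**Inputs**

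- n = participants enrolled. For illustration n = 50, from Section 3.6 ("A sample size of 25 patients in each group was chosen", so 2 × 25 = 50).
- N = eligible patients. The protocol does not state N, so it is varied.
- Assumption for the illustration: every eligible non-participant is counted as a refuser, so refusers = N − n.

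**Formulas**

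- Literal 7.1 rate: R = n / (N − n).
- Proportion in Section 2.1 and the progression rule: p = n / N.
- Hence R = p / (1 − p) and p = R / (1 + R). R exceeds 100% whenever p exceeds 50%.

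**Conversions at the threshold**

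- p = 0.60 gives R = 0.60 / 0.40 = 1.50, that is 150%.
- R = 0.60 gives p = 0.60 / 1.60 = 0.375, that is 37.5%.

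**Illustration with n = 50**

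| Eligible N | Refusers N − 50 | Proportion p | Literal R | p > 60%? | R > 60%? |
|---|---|---|---|---|---|
| 83 | 33 | 60.2% | 151.5% | yes | yes |
| 84 | 34 | 59.5% | 147.1% | no | yes |
| 100 | 50 | 50.0% | 100.0% | no | yes |
| 101 | 51 | 49.5% | 98.0% | no | yes |
| 133 | 83 | 37.6% | 60.2% | no | yes |
| 134 | 84 | 37.3% | 59.5% | no | no |

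The two measures fall on opposite sides of 60% for N = 84 to 133. From 84 to 99 the literal value is above 100% and would look wrong at once. From 101 to 133 it is an ordinary-looking percentage.

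**Does reading in the missing participants repair it?** The natural repair is participants / (participants + refusers). Section 4 describes an e-Boks invitation, with a telephone call only to patients who accept it. A patient who never responds has neither joined nor clearly refused. With assumed counts of 50 enrolled, 30 refusing and 20 not responding, this repair gives 50 / 80 = 62.5%, while the proportion of all eligible patients is 50 / 100 = 50%. The denominator therefore has to be spelled out.

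**The case against.** The strongest reply is that this is a slip with no consequence. The phrase used in 7.1 normally introduces a group that contains the numerator. Since participants cannot be among refusers, the sentence contradicts itself and hardly amounts to a rival formula. A few words have probably dropped out. Section 2.1 and the progression rule both say what is meant, and Section 9.1 lists the eligible count among its process measures, so an error would be easy to detect. Most of this stands: the wording is probably unintended, and the odds is only what results from following it literally. What remains is that the defective sentence is the only explicit formula for a primary outcome.

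Two stronger readings are tempting, and the documents support neither.

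- A reader might infer that the go/no-go decision is wrong. The progression rule is expressed in eligible patients, so the decision fails only if someone substitutes the 7.1 rate for the quantity that the rule names. The range of 84 to 133 depends on that substitution, on exactly 50 enrolled and on all non-participants being refusers. With no expected number of eligible patients, it says nothing about likelihood.
- A reader might infer that the definition also clashes with the other 60% statement in 7.1, "A proportion of 60% or more of patients awaiting elective CABG surgery who are eligible for the study is acceptable". That sentence has no verb of participation and could even be read as the share of waiting patients who are eligible. It is too loose to count as a clear contradiction.

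**Conclusion.** The definition in 7.1 is wrong as written and contradicts Section 2.1 and the progression rule at the end of 7.1. Followed literally, it overstates recruitment at every level of uptake above zero: 60% becomes 150%, and a literal 60% is 37.5%. These conversions need only the assumption that eligible patients are participants plus refusers.

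The misreporting of the outcome follows directly from using the written formula. An effect on the decision to proceed is conditional on comparing that figure with 60%, and the progression rule's own wording points away from doing so. This is a definition that should be corrected before results are tabulated, not evidence that the progression rule is invalid. The 30% figure under Adherence in 7.1 is a separate matter and carries no weight here.

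**What to change.** In Section 7.1, define recruitment rate = participants enrolled / all patients assessed as eligible at screening, and state that the denominator includes those enrolled, those who declined, those who did not respond and those who were not approached. This matches Section 2.1 and the progression rule. State that this is the rate held against the 60% criterion, and name the same denominator for the participation rate in Section 9.1. Uptake among approached patients may be added as a separate figure. It should not replace the main rate, because its denominator is narrower than all eligible patients.

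The cost is wording. The surgeon already screens referrals for eligibility (Section 4) and may review records for that purpose without consent (Section 8.2). Section 9.1 already plans the number eligible and the reasons for non-participation. The screening log has to separate non-responders and patients not approached from decliners. The one drawback is that the reported rate will be less favourable than under the written formula.

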4.1 Inclusion criteria

- Planned to have elective isolated first-time CABG surgery.
- 18 years or older
- Two weeks or more prior to surgery
- Speaks and understands Danish.
- Gives written informed consent.

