6.2.1 Exercise intervention

During the initial assessment patients will be taught how to perform the exercises to complete at home during the intervention period. The exercise intervention is supervised by skilled physiotherapists and delivered via Infinity Connect app and a webcam⁷² at Rigshospitalet to a group of approximately 4–8 patients who exercise at home and communicate via a tablet. Each session is 60 min, i.e., 40 min of exercise and 20 min of patient education, three times per week for the prehabilitation period. The exercises used in the program are identified and selected amongst exercises used in previous exercise intervention studies and involves larger muscle groups with 50/50% exercises for upper and lower extremities, respectively.⁷³ The exercises are executed in four sets to achieve peripheral muscle fatigue and secondary dyspnea/breathlessness. Each set is carried out in a predefined period of 20 to 40 s with a maximum number of repetitions performed, i.e., 8 to 25 repetitions depending on the patients exercise capacity and motivation, but with the aim of 12 to 20 repetitions.^{73,74} In practice the training intensity is determined by using the self-rated Borg Scale, moderate intensity RPE 11-15, 50-60% VO₂peak.⁷⁴

The first week serve as a familiarization phase with the purpose to adapt to exercising, adjusting, and optimizing load and to avoid musculoskeletal overload injuries. Monitoring physical activity and providing motivation through phone calls weekly will be enhanced by incorporating a novel accelerometer system, offering activity level feedback (SENS innovation)⁷⁵ to guide healthcare staff. Participants in the intervention will be instructed to perform daily exercise tasks such as brisk walking and sit-stand exercises. Additionally, motivational phone calls will be made to participants in the intervention group, while healthcare staff will receive feedback on these patients, aiding to guide them in achieving their activity goals. Patients will also be asked to complete a diary describing physical activity outside the programmed session, included in a patient booklet. All study participants will wear the accelerometer from the screening phase until the day preceding the procedure, and again postoperatively until the day of discharge and for 30 days

thereafter.^{76,77} The technology platform provided to the patients includes a tablet and an accelerometer device to facilitate exercise training sessions and data collection.

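### The pooled adherence ratio in section 7.1 reaches 75% with no nurse call taken, so it cannot show adherence to all components of the programme

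*Protocol*

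**What the plan says.** Among the objectives in section 2.1 is to assess adherence and completion, explained as: "do participants adhere and work through all components of the intervention". Sections 6.2.1 to 6.2.5 describe five components: exercise, nutrition, psycho-education, smoking cessation and alcohol cessation.

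The weekly contacts are set at the end of section 6.2.5: "three web-based sessions with a physiotherapist and one telephone counselling with a nurse per week during the intervention period". For the tele-sessions, section 6.2.1 adds: "Each session is 60 min, i.e., 40 min of exercise and 20 min of patient education, three times per week". After baseline, psycho-educative consultations take place "once a week (by phone) in the waiting period until the day before surgery" (section 6.2.3). Smoking cessation consists of "counselling sessions at baseline and weekly phone call sessions" (section 6.2.4). Sections 6.2.2 and 6.2.5 mention adherence support for nutrition and alcohol but describe no separate weekly contact for either.

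Section 7.1 measures adherence to the interventions as the "number of telephone counselling and tele-exercise sessions delivered out of the theoretical number that could have been delivered", given each participant's wait. Three participant-level thresholds follow:

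- more than 70% of the prescribed exercise programme, self-reported, with an added reference to phone calls;
- 70% or more of planned sessions, to be reached by at least 70% of participants;
- as a condition for a larger trial, "at least 52% of the intervention group will receive more than 60% of the intended interventions".

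None of the three expressly sets a minimum number of nurse calls.

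**The concern.** The ratio gives every contact the same weight, and three of every four contacts are tele-exercise. Most of the scheduled follow-up for the other components sits in the fourth. A high score can therefore arise when the calls were hardly taken up at all. Supplements for nutritionally at-risk patients, nicotine replacement and sessions with the social nurse enter neither numerator nor denominator.

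The figure feeds the decision on a full-scale trial. A pass could be reported as showing that multimodal prehabilitation is feasible when it shows only that tele-exercise was attended. The objective on all components would remain unanswered, and the next trial could carry forward a counselling component that patients do not use.

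**Working it through.** The protocol states no figure for this, so there is none to reproduce.

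**Inputs.** Three tele-sessions and one call per week (end of section 6.2.5). Minimum wait: "Two weeks or more prior to surgery" (section 4.1). Recommended maximum wait: 30 days (section 10.3.1). Intervention arm: 25 patients (section 3.6). Thresholds: section 7.1.

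**All tele-sessions, no calls.** For a wait of w whole weeks the score is 3w / (3w + w) = 3/4.

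- 2 weeks: 6/8 = 75%
- 3 weeks: 9/12 = 75%
- 4 weeks: 12/16 = 75%

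Counting the attended baseline visit as a contact changes little: 7/9 = 77.8% at 2 weeks and 13/17 = 76.5% at 4 weeks. The reverse pattern, all calls and no tele-sessions, scores 25%.

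**Part-weeks.** For waits of 14 to 60 days, with planned sessions (3 × days / 7) and calls (days / 7) each rounded up or down, the score lies between 66.7% and 81.8%. It is below 70% only at 15–16 days (6/9 = 66.7%) and 22–23 days (9/13 = 69.2%), and only if sessions round down while calls round up. It never falls to 60%.

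**Exercise attendance needed when no calls are taken.** If a share e of tele-sessions is attended, the score is 0.75e.

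- 70% of planned sessions: e ≥ 0.70/0.75 = 93.3%
- more than 60%: e > 0.60/0.75 = 80%

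Missing one tele-session gives 5/8 = 62.5%, 8/12 = 66.7% and 11/16 = 68.8% at 2, 3 and 4 weeks. Each fails the 70% rule and passes the 60% rule.

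**Arm level.** The rules need 0.70 × 25 = 17.5, hence 18 patients, and 0.52 × 25 = 13 patients. Counted in sessions at whole-week waits, both would be met if that many attended every tele-session and took no call.

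**Unit of the go/no-go condition.** In sessions, the all-tele-sessions participant scores 75% and passes. Counted as the five components of section 6.2, exercise alone is 1/5 = 20% and fails. The wording does not settle which applies.

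**Scored by delivery mode**, the same participant has 100% of tele-sessions and 0% of calls, so the gap is visible.

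**The case against.** A reader might infer that someone who only exercises passes every adherence rule, whatever the length of the wait. The protocol does not support that.

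- The more-than-70% target is based on the exercise programme, so pooling does not affect it. If its added words on phone calls are a second requirement rather than a data source, a participant who takes no calls fails it.
- The go/no-go condition counts an undefined unit, and by component the same participant fails.
- 75% is exact only for whole-week waits, and section 6.1 says surgery dates are tentative.
- The 70% rule needs near-perfect tele-session attendance when no calls are taken.

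Nor do the non-exercise components lose all support without the calls. Tele-sessions include 20 minutes of education, hazardous drinkers are offered sessions with the social nurse, at-risk patients are offered supplements, smokers are directed to municipal services, and participants have a nurse's telephone number. The weekly calls also serve exercise motivation.

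These points narrow the claim but do not remove it. None of this other support enters the adherence ratio. The interviews explore engagement, and smoking and alcohol status are recorded as outcomes, but neither measures uptake of the calls.

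It can also be said that a breakdown by delivery mode is tabulation detail that an analysis plan may supply, and that the protocol does not forbid it. That is fair for reporting. But the protocol itself fixes the ratio and the thresholds, and a later table would not change a decision rule that leaves its unit open.

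**Conclusion.** The point holds in limited form. With the ratio read as pooled, which is its plain sense, full tele-session attendance and no calls scores 75% at whole-week waits and about 67% to 82% with part-week rounding. That satisfies the planned-sessions rule at whole-week waits. If the go/no-go condition is counted in sessions, the only unit that section 7.1 defines, it is satisfied too, and just over 80% of tele-sessions is then enough. The pooled figure therefore cannot answer the section 2.1 objective on all components.

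How often participants would behave this way is unknown, and the protocol gives no basis for an estimate. The study is descriptive and small, so the matter is one to correct before the go/no-go decision and does not threaten the design.

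**What to change.** In section 7.1:

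1. Compute and report adherence separately for tele-exercise sessions and nurse calls. The pooled figure may stay as a supplement.
2. Report uptake of supplements, nicotine replacement and social-nurse sessions among those to whom each applies. Ask about it at the assessment on the day before surgery as well as in the calls, so that it is not missing for those who took no calls.
3. State what the go/no-go condition counts, in a form that cannot be met with no nurse calls taken.

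A minimum for calls should be a number of calls, not automatically 70% in each mode. Waits between two weeks and 30 days hold about two to four calls. Under a 70% rule one missed call would fail a participant at 2 weeks (1/2 = 50%) or 3 weeks (2/3 = 67%) but not at 4 weeks (3/4 = 75%), even with full exercise attendance.

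The cost is a tabulation of contacts already planned and a few questions at existing contacts, with no added visits. The downsides are that reported adherence may be lower and that call adherence is a coarse measure with so few calls.
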